1.3.3 Hyaluronan is an important driver of respiratory disease and pulmonary hypertension

Hyaluronan (HA), also known as hyaluronate or hyaluronic acid, is a glycosaminoglycan and a major component of the lung ECM^{24,25}. Elevated hyaluronan has been reported in lung diseases including IPF and PAH²⁶⁻³⁰ and in PH associated with chronic obstructive pulmonary disease³¹. Furthermore, overexpression of hyaluronan synthase 2 (HAS2), an enzyme responsible for the synthesis of hyaluronan, has been implied in severe fibrosis²⁹. In addition, increased hyaluronan has also been reported in autoimmune diseases. For example, in systemic sclerosis (SSc), elevated HA is present in both the skin³² and associated with lung injury^{33,34}. Elevated HA appears to be associated with progressive SSc affecting the lungs where it is associated with fibrosis³⁵ and in patients with connective tissue disease (CTD) associated ILD³⁶. These are consistent with increased HA observed in patients with Group 1 PH²⁶. Collectively, these studies point at a pathogenic role of HA in the PH associated with chronic lung diseases and suggest that therapies targeting HA may serve as novel disease-modifying treatments for PH.

The inflammatory effects of HA are dependent on its molecular weight. High molecular weight HA (HMW-HA) of 1000 KDa is believed to have protective effects³⁰. However, the breakdown of HA into low molecular weight (LMW) HA has been demonstrated to contribute to its pathobiological effects in the lung³⁰. In line with this, increased LMW-HA fragments have been detected in an experimental model of PH associated with lung fibrosis².

1.3.4 H01 is a novel approach to addressing pulmonary hypertension secondary to interstitial lung disease

H01, also known as 4-methylumbelliferone (4MU), is a small molecule inhibitor of HA synthesis. H01 reduces HA levels primarily through two identified mechanisms. The first mechanism occurs through the extensive glucuronidation of H01 by UDP-glucuronyltransferases (UGTs) resulting in the depletion of UDP-glucuronic acid, one of the two substrates required for HA synthesis^{37,38}. The second way that H01 reduces HA levels is by downregulating HAS mRNA levels³⁹. 4MU has been shown to inhibit HA production in multiple cell lines and tissue types⁴⁰⁻⁴⁴. 4MU has also been used in multiple animal models of cancer, fibrosis and autoimmunity^{39,45-51}. Several studies have demonstrated that inhibition of HA using H01 prophylactically and therapeutically attenuated features of experimental PH including vascular remodelling and elevated right ventricle systolic pressure (RVSP, a surrogate for mPAP in mice). Using a mouse model of lung fibrosis and PH studies showed that a 2-week oral treatment with H01 inhibited RVSP and vascular remodelling². These results were replicated in a mouse model exhibiting lung fibrosis, PH and airspace enlargement, where H01 treatment for 4 weeks was able to attenuate vascular remodelling and RVSP values³. Interestingly, in these studies, lung fibrosis was also attenuated. In addition to these highly-relevant pre-clinical studies in models that recapitulate features of Group 3 PH, H01 has been shown to be effective in models of acute lung injury^{5,6}.

In addition, H01 has demonstrated anti-fibrotic activity in other settings of inflammation (e.g., liver fibrosis). Independent of H01, HA inhibition has also been linked directly with meaningful clinical outcomes such as Forced Expiratory Volume (FEV1) in respiratory disease⁵². Taken together, these results point at elevated HA as a key feature in patients and experimental models of pulmonary hypertension. Furthermore, preclinical studies using H01 both prophylactically therapeutically demonstrates a beneficial effect of H01 in treating PH associated with lung fibrosis. These results underscore the use of H01 as a novel agent to treat Group 3 PH, where limited treatment options are available.

Hymecromone (H01; 4-methylumbelliferone), a known inhibitor of HA synthesis, has been studied pre-clinically in inflammation and fibrosis⁵³⁻⁵⁵. In particular, H01 is of benefit in multiple models of airway inflammation^{5,6,56}. Including in multiple pre-clinical mouse models of PH^{2,13}. Hymecromone is an approved oral drug in Europe (European Union reference date [EURD] 07/27/1965) indicated in various diseases of the gallbladder and biliary tract (i.e. Biliary dyskinesia). It is hypothesized that its mechanism of action in biliary dyskinesia and autoimmunity may work, in part, via inhibition of hyaluronan biosynthesis. In regards to inhibition of HA, H01 is extensively glucuronidated by UDP- glucuronyltransferases (UGTs) which results in the depletion of UDP-glucuronic acid, a precursor necessary for HA synthesis.^{37,38} There is substantial evidence for the efficacy and safety of H01 based on its approved uses in multiple markets and

The SATURN Study [CONFIDENTIAL – DO NOT REDISTRIBUTE]

in multiple clinical trials⁵⁷. A comprehensive review of H01 is available³⁹.

We propose a Phase 2a study of H01 in patients with Group 1 and Group 3 Pulmonary hypertension. This proof-of-concept study will generate data supporting the ultimate goal of investigating H01 as a safe, effective, oral treatment for patients with pulmonary hypertension.

2 H01 PHARMACOLOGY

2.1 Dose Rationale

H01 is an approved oral drug in Europe (European Union reference date [EURD] 07/27/1965) for disorders of the biliary tract. H01 has been administered chronically in humans for 50+ years at doses up to 1800 mg/day PO with few observed adverse safety events. Based on the European package insert, the standard dosing regimens for adults in hepatobiliary conditions are 300-600 mg oral up to 3 times / day (900-1800 mg/day).

Several clinical trials of H01 in humans have been published and all demonstrated safety during both short and long-term administration (Appendix B). The longest reported duration of administration was a study of oral administration for 6 months in patients (n=29)⁵⁸. The highest dose administered in a clinical trial is 3600mg for 4 days.

To inhibit excess HA synthesis and alleviate respiratory distress, we propose to administer H01 800mg twice a day (1600 mg/day) PO for 24 weeks. Twice daily dosing was selected to facilitate outpatient adherence. If the participants are enrolled in the open-label extension, H01 is administered twice a day at dose of 800 mg (1600 mg/day) until Week 48.

The selected dose of 1600 mg/day is consistent with non-clinical models of lung injury where human equivalent doses (HED) of H01 ranging from 120 mg/day PO to 2600 mg/day intra-peritoneal (IP) demonstrate notable functional improvements and reduced HA in bronchoalveolar lavage fluid^{2,5,6}. In the Phase 1 dose range study recently completed at Stanford University, doses of 1200mg, 2400mg and 3600mg per day doses over 4 days in healthy volunteers were well tolerated and led to decreases in sputum HA.

Given the existing body of safety data for H01, and the relevance of the models suggesting 2600mg/day IP, characteristics of H01's pharmacology, and the time necessary to see clinical efficacy in pulmonary hypertension patients, the decision was made to target 1600mg/day for 24 weeks. A BID regimen is selected over a QID regimen primarily to support patient compliance over a 24-week period. Participants enrolled in the open-label extension until week 48 will continue this BID regimen (800 mg twice a day).

The results at this dose will inform the H01 development plan and larger scale dose-range studies.

2.2 Clinical Efficacy

Dozens of previous studies of H01 have established efficacy in the context of approved and currently marketed indications (hepatobiliary conditions)(reviewed in Nagy 2015³⁹) A recently completed Phase 1 dose-range study demonstrated inhibition of hyaluronan in the sputum of healthy adults over 4 days (pharmacodynamic marker).

The current study will be the first study to use the novel mechanism of HA inhibition to investigate the clinical efficacy in pulmonary hypertension.

2.3 Clinical Safety

In published clinical trials including more than 200 patients, H01 has demonstrated safety with over 28 patient years of exposure. In these studies, H01 was safe and well tolerated. The safety profile of H01 is supported further by decades of marketing authorization approval in Europe, which is characterized by broader pharmacovigilance data. A principal European manufacturer reports awareness of more than 60 clinical trials including 2638 patients (Grunenthal 2020). The main reported side effects for H01 in the product labels include diarrhea and allergic reactions. According to the WHO spontaneous reporting database⁵⁹, investigated on August 8th, 2021, only 63 cases of adverse drug events to H01 have been reported since 1967 worldwide. The majority of reported adverse events concerned skin disorders (42.9%, mainly urticaria and pruritus), GI disorders (20.6%, mainly diarrhea), and immune system disorders (20.6%, mainly anaphylactic shock, angioedema or face edema).

In fourteen randomized controlled trials, few side-effects were reported at doses up to 2400 mg/day PO^{39,60}. In another study of H01 at 2400 mg/day in patients following surgical revision of biliary pathways, no serious adverse reactions were observed.

2.4 Non-clinical Efficacy

H01 has been studied in multiple animal models of lung injury. Across these animal models, inhibition of HA synthesis with H01 led to a significant reduction in HA content, as well as clinically relevant outcomes. Five relevant studies are summarized below:

- **Bleomycin model of pulmonary hypertension and lung fibrosis.** In 2017, Collum *et al.* published an article entitled “Inhibition of HA synthesis attenuates pulmonary hypertension associated with lung fibrosis”². In an experimental model of lung fibrosis and pulmonary hypertension (PH), mice were treated i.p. with 0.035 U/g of bleomycin (BLM) or vehicle (PBS) twice a week for 4 weeks. This model of chronic injury presents with fibrotic deposition affecting the distal areas of the lung, which is more representative than the more common intra-tracheal (IT) instillation of bleomycin. On day 15, mice were provided with chow containing H01 at a dose of 20 mg/kg/day or regular chow for the remainder of the experiment. To deliver 20 mg/kg/day, H01 was added to the diet at a concentration of 125 mg/kg diet (assuming a mean body weight ~25 g and chow intake ~4 g per day). It was observed that blood oxygenation was reduced by 25% in the bleomycin-exposed mice on control chow, whereas only 5% oxygenation reduction was observed in the bleomycin-exposed and H01 treated group. This was consistent with improvised right ventricle systolic pressure (RVSP) values in BLM-exposed and H01 treated mice compared to BLM-exposed vehicle treated mice. RVSP is a surrogate value for mPAP in mice. Furthermore, hyaluronan (HA) levels observed by immunohistochemistry (IHC) showed increased HA deposition in bleomycin-exposed mice that were inhibited by H01 therapy. In line with this, bronchoalveolar lavage fluid (BALF) revealed a significant HA elevation in bleomycin-exposed mice that was attenuated from 1600 ng/mL HA to 1000 ng/mL HA by H01 treatment. These

observations were consistent with increased levels of the HA-synthases Has1, Has2 and Has3 expression in bleomycin-exposed mice. H01 attenuated Has2 and Has3 but not Has1 expression.

- **Adenosine deaminase null mouse (Ada^{-/-}) model of lung fibrosis and pulmonary hypertension in combined pulmonary fibrosis and emphysema (CPFE).** In 2019, Collum *et al.* published an article entitled “Adenosine and hyaluronan promote lung fibrosis and pulmonary hypertension in combined pulmonary fibrosis and emphysema”³. Genetically engineered mice lacking adenosine deaminase (Ada^{-/-}) were utilized as an experimental model of lung fibrosis and pulmonary hypertension (PH) in combined pulmonary fibrosis and emphysema (CPFE). Ada^{-/-} mice received supplemental PEG-ADA, allowing them to live normally, from birth up to week 24. Starting on week 24, PEG-ADA was gradually reduced over 9 weeks and, starting on week 34, mice were provided with either control chow or medicated chow (H01 at a dose of 20 mg/kg/day) for 4 weeks. Ada^{-/-} mice developed increased fibrosis in the lung as detected by Masson’s trichrome staining for collagen which was decreased upon H01 treatment. Arterioles from Ada^{-/-} mice exhibited increased aSMA staining indicative of increased muscularization of the arterioles which resulted in an increased smooth muscle area/vessel ratio. Arterioles from H01-treated Ada^{-/-} mice had significantly decreased aSMA staining and a more normalized smooth muscle area/vessel ratio. Ada^{-/-} mice also had significantly decreased levels of arterial oxygenation (SpO₂) which were normalized with H01 treatment. Importantly, bronchoalveolar lavage fluid (BALF) levels from Ada^{-/-} mice contained HA levels that were significantly increased (> 10x) compared to normal mice while H01 treatment in Ada^{-/-} mice were only ~3x above normal. In addition, in this study H01 was able to therapeutically reduce evidence of fibrotic matrix remodeling in these mice.
- **Hypoxia-induced Pulmonary Hypertension.** In an unpublished study using mice lacking HAS2, investigators demonstrate that these mice are protected from the development of pulmonary hypertension, induced following chronic exposure to hypoxia (10% O₂ for 28 days) with weekly Sugen (SU5416) injections. Similarly, in a model of hypoxia-sugen induced pulmonary hypertension, H01 administered starting on day 15 of 10% O₂ halted vascular remodeling, perivascular HA accumulation and attenuated RVSP after 13 days of treatment. The hypoxia-sugen model of PH is able to recapitulate some of the features of patients with PAH, including elevated RVSP and vascular wall thickening without parenchymal lung disease. These studies underscore the role of HA synthesis in PH and highlight the capacity of H01 to halt the development of disease.
- **Staphylococcus enterotoxin B (SEB)-induced model of acute lung inflammation.** In 2013, McKallip *et al.* published an article entitled “Treatment with the hyaluronic acid synthesis inhibitor 4-methylumbelliflerone suppresses SEB-induced lung inflammation”⁵. The effects of H01 on staphylococcus (SEB)-induced acute lung inflammation were investigated *in vitro* and *in vivo*. Culturing staphylococcal enterotoxin B (SEB)-activated immune cells with H01 led to reduced proliferation, reduced cytokine production as well as an increase in apoptosis when compared to

untreated cells. In an *in vivo* model of lung inflammation, exposure to SEB led to significantly elevated levels of 1500 pg/mL hyaluronan (HA) in the bronchoalveolar lavage fluid (BALF). However, H01 treatment following SEB exposure significantly reduced BALF HA levels to 200 pg/mL. Concomitant with the decrease in BALF, HA levels, mRNA levels of HAS1, HAS2 and HAS3 were also all significantly decreased. Furthermore, exposure of vehicle-treated mice to SEB led to an increase in the expression of various cytokines, such as IL-1 β , IL-2, IL-6, IFN- γ , and TNF- α , which are all reported to play a role in lung inflammation. In comparison, treatment of mice with H01 led to a significant reduction in the SEB-induced increase in all cytokines measured.

- **Lipopolysaccharide (LPS)-induced model of acute lung inflammation.** In 2015, McKallip *et al.* published an article entitled “Treatment with the hyaluronic acid synthesis inhibitor 4-Methylumbelliferon suppresses LPS-induced lung inflammation”⁶. The effects of H01 on lipopolysaccharide (LPS)-induced acute lung inflammation were investigated *in vitro* and *in vivo*. Culturing LPS-activated immune cells with H01 led to reduced proliferation, reduced cytokine production, and an increase in apoptosis when compared to untreated cells. Treatment of mice with H01 (single dose of 450 mg/kg i.p., approximately 18000 mg/kg assuming a body weight of 25 g) led to protection from LPS-induced lung injury. Specifically, H01 treatment led to a reduction in LPS-induced HA synthase (HAS) messenger RNA (mRNA) levels HAS1 decreased from 9 to 1.5, HAS2 from 8 to 0.5, HAS3 from 13 to 1. Vascular permeability induced by LPS was reduced nearly 4-fold with H01 treatment while pro-inflammatory cytokine levels (IL-6, IFN- α and IFN- γ) were reduced by >90% with treatment.

[figure not shown]
2.5 Non-clinical Safety

The acute toxicity of H01 is relatively low: the LD50 for oral administration is 7593 mg/kg in mice and 6220 mg/kg in rats (highest doses tested; HED 37,000 mg/day and 61,000 mg/day, respectively). Protracted oral administration of 800-2400 mg/kg/day for 3 months in a dog model (HED 79,000 mg/day) and of 400-1000 mg/kg/day for 4 months in a rat model (HED 9700 mg/day), showed no toxicities in physical or behavioral measures (Cantabilin Label Italy - Attachment). No teratogenicity was observed in rat or rabbit at oral doses up to 1200 mg/kg/day (HED 23,000 mg/day). Toxicology tests on animals have not shown any toxic phenomena, abnormalities of growth or behavior. No cases of teratogenicity or fetal toxicity have been encountered.

2.6 Hypothesis

We hypothesize that oral H01 at doses of 1600 mg per day for 24 weeks in the blinded study and for an additional 24 weeks as part of open-label extension will be safe and well-tolerated and show evidence of clinical efficacy. We will conduct exploratory analyses in both the blinded study and open-label extension to further establish the correlation of changes in serum HA with meaningful clinical outcomes.

3 STUDY DESIGN

** For participants not participating in the open-label extension

*** For participants participating in the open-label extension

† (Week 24) of the blinded study and through Week 48 of the open-label extension

3.1 Study Treatment

Participants will be randomized approximately 5:3 (Treatment:Placebo). Participants randomized to treatment will be given 800 mg oral H01 two times a day (total dose: 1600 mg/day). Participants randomized to placebo will receive oral tablet placebo (inactive ingredients) two times a day. Participants will be on treatment continuously for 24 weeks or 48 weeks if enrolled in the open-label extension. During the treatment period, participants will be monitored according to the schedule of assessments below. Participant a follow up will take place 30 days after the end of treatment at Week 24 if not enrolled in the open-label extension.

4 ENDPOINTS

4.1 Primary Endpoint

- Change in pulmonary vascular resistance (PVR) measured by right heart catheterization (RHC) from baseline to end of treatment (Week 24) of the blinded study

4.2 Secondary Endpoints

- The safety and tolerability of H01 in adults with pulmonary hypertension using the Common Terminology Criteria for Adverse Events (CTCAE)
- Change in mean pulmonary arterial pressure (mPAP) by RHC from baseline to end of treatment (Week 24) of the blinded study
- 6 Minute Walk Distance Test (6 MWDT) from screening to end of treatment (Week 24) of the blinded study or through Week 48 of the open-label extension
- Change in quality of life (QOL) score, EMPHASIS-10 score and St George Respiratory Questionnaire (SGRQ) score from baseline to end of treatment (Week 24) of the blinded study or through Week 48 of the open-label extension
- Change in serum HA concentration from baseline to end of treatment (Week 24) of the blinded study or through Week 48 of the open-label extension
- Change in NT-proBNP from baseline to end of treatment (Week 24) of the blinded study or through Week 48 of the open-label extension

4.3 Exploratory Endpoints

- Change in inflammatory markers and PH-specific biomarkers (ESR, HSCRP)
- Change in pro-inflammatory cytokines
- Change in Forced Expiratory Volume in one second (FEV1)
- Change in Forced Vital Capacity (FVC) from pulmonary function test (PFT)
- Change in Total Lung Capacity (TLC) from pulmonary function test (PFT)
- Change in Lung diffusion capacity (DLCO) from pulmonary function test (PFT)
- Change in exhaled breath condensate (EBC) hyaluronan concentrations over the study period
- Describe the pharmacokinetics (H01 and metabolite serum concentrations)
- Describe HA fragment size

5 STUDY POPULATION

Adults with Group 1 PAH secondary to connective tissue disease, idiopathic, hereditary, toxins, or drugs and adults with Group 3 PH secondary to interstitial lung disease. Individuals interested in participating in the study will be screened for inclusion and exclusion criteria. If the patient meets criteria and consents to participate, they will be enrolled and undergo randomization.

5.1 Inclusion Criteria

- Adults age 18 to 75 years inclusive;
- WHO functional class II/III/IV despite treatment with maximally tolerated doses of 2 or more treatment modalities including PDE5 inhibitors, guanylate cyclase stimulators, endothelin receptor antagonists, and prostanoids when appropriate.
- Baseline 6MWT > 100 meters and < 550 meters
- Established diagnosis of Group 3 pulmonary hypertension secondary to interstitial lung disease OR established diagnosis of Group 1 pulmonary hypertension secondary to connective tissue disease, idiopathic, hereditary, drugs, or toxins.
- Right heart catheterization at randomization showing precapillary pulmonary hypertension (mPAP \geq 25 mmHg and PVR \geq 400 dynes * sec * cm⁻⁵) and:
 - PCWP \leq 20 mmHg for Group 3 PH patients and Group 1 PAH patients
- Participants on chronic medication for PAH, PH, or underlying lung disease must be on a stable and optimized dose for at least 90 days prior to the first dose of the study drug.
- Female participants who are heterosexually active must use an acceptable method of contraception: condoms (male or female) with or without a spermicidal agent, diaphragm or cervical cap with spermicide, IUD, or Hormone-based contraceptive
- Be able to provide written informed consent and comply with requirements of the study

5.2 Exclusion Criteria

- Participants with a diagnosis of PAH or PH for reasons other than the pulmonary hypertension *primarily* due to any of the following:
 - Group 2, 4, or 5
 - Group 1 due to HIV, veno-occlusive disease, porto-pulmonary hypertension, congenital heart disease
 - Group 3 due to severe chronic obstructive pulmonary disease (COPD) or obstructive sleep apnea (OSA)
 - Note: participants with overlapping syndromes will be evaluated on a case-by-case basis by the recruiting physician
- Total Lung Capacity (TLC) < 60% predicted
- FEV1/FVC < 50% predicted or FEV1 < 55% predicted
- Inability to safely attempt completion of the 6MWD test
- Use of experimental PAH treatments within the past 3 months
- Current systemic treatment with hymecromone
- Left sided heart disease as defined by either a PCWP > 20 mmHg and/or left ventricular ejection fraction < 40%
 - Note: participants with abnormal left ventricular function attributable entirely to impaired left ventricular filling due to the effects of right ventricular overload (ie right ventricular hypertrophy and/or dilatation) are not excluded

The SATURN Study [CONFIDENTIAL – DO NOT REDISTRIBUTE]

- Participants must not have 3 or more of the following left ventricular disease / dysfunction risk factors:
 - Body mass index (BMI) $\geq 30\text{kg}/\text{m}^2$
 - History of essential hypertension requiring medication
 - Diabetes mellitus
 - Historical evidence of significant coronary disease established by any of the following:
 - History of myocardial infarction
 - History of percutaneous coronary intervention or coronary artery bypass graft
 - Angiographic evidence of $>50\%$ stenosis in at least one coronary artery
 - Positive stress test with imaging
 - Stable angina
- Significant valvular heart disease as determined by more than moderate findings on echocardiogram or history of valve replacement
- Pregnant or actively breastfeeding
- Female participants with childbearing potential not willing to use a form of birth control (including abstinence) during the study
- Inability to undergo right heart catheterization
- Acute pulmonary embolism within 90 days of randomization
- Exacerbation of underlying lung disease or active pulmonary or upper respiratory infection within 30 days of randomizations
- Use of any inhaled tobacco products or significant history of drug abuse within 3 months prior to randomization
- Subject is receiving $>10\text{L}/\text{min}$ of oxygen supplementation by any mode of delivery at rest at baseline
- Body mass index $\geq 40\text{kg}/\text{m}^2$
- Participants with history of dysphagia, achalasia, or difficulty swallowing capsules, tablets or pills
- Participants with liver failure or AST or ALT greater than 2 times the upper limit of normal
- Participants with total bilirubin levels greater than 2 times the upper limit of normal
- Participants with CrCl <45
- Use of any investigational drug/device, or participation in any investigational study with therapeutic intent within 30 days prior to randomization
- Known allergy to hymecromone or any component of drug product (including rare hereditary problems of galactose intolerance, Lapp lactase deficiency, or glucose-galactose malabsorption)
- Known allergy to any component of placebo (including rare hereditary problems of galactose intolerance, Lapp lactase deficiency, or glucose-galactose malabsorption)
- Physician concern that participant may not adhere to the study protocol
- Significant psychiatric, addictive, or other disorder that compromises the subject's ability to provide informed consent

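### The stem of the first exclusion in Section 5.2 is worded in reverse: read literally, it excludes the target population and spares the non-target causes it lists

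*Combined protocol and SAP*

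**What the plan says.** Three places define the population in the same way. The study population entry in Section 1.2 and the statement in Section 5 both name Group 3 PH from interstitial lung disease (ILD) and Group 1 disease from five causes; Section 5 puts the Group 1 part as "Adults with Group 1 PAH secondary to connective tissue disease, idiopathic, hereditary, toxins, or drugs". Section 5.1 makes this a criterion: "Established diagnosis of Group 3 pulmonary hypertension secondary to interstitial lung disease OR established diagnosis of Group 1 pulmonary hypertension" from those same five causes.

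Section 5.2 then opens by excluding "Participants with a diagnosis of PAH or PH for reasons other than the pulmonary hypertension", continues with an italicised 'primarily', and points to a list. The list has three items: Groups 2, 4 or 5; "Group 1 due to HIV, veno-occlusive disease, porto-pulmonary hypertension, congenital heart disease"; and Group 3 from severe COPD or OSA. A note under the list adds that "participants with overlapping syndromes will be evaluated on a case-by-case basis by the recruiting physician".

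**The concern.** The words 'other than' turn the rule round. The list contains only causes the trial does not want, so a stem that excludes PH for reasons other than those causes excludes the causes the trial does want. An exclusion criterion is operative text: it is what an eligibility checklist is built from and what a monitor checks against. Here it contradicts Sections 1.2, 5 and 5.1.

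What is at stake is narrow. Mixed causes are foreseeable: Section 1.3.2 says the PH groups can overlap and names COPD, ILD and OSA as the commonest lung diseases leading to PH. For a patient with a target diagnosis and a coexisting listed cause, someone has to decide which cause is primary and what follows from that. This bullet is where the protocol should say so.

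**Working it through.** There is no figure in the plan to reproduce. The check passes each cause of PH through two criteria only, the diagnosis criterion in 5.1 and the first exclusion in 5.2, first as worded and then in the direction its list implies.

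Inputs:
- Target causes (Sections 1.2, 5 and 5.1): ILD, connective tissue disease, idiopathic, hereditary, drugs, toxins. That is 1 + 5 = 6.
- Listed causes (Section 5.2): Groups 2, 4 and 5 (3); HIV, veno-occlusive, porto-pulmonary and congenital heart disease (4); severe COPD and OSA (2). That is 3 + 4 + 2 = 9.

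Patients with a single cause:

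| Cause | 5.1 diagnosis | 5.2 as worded | Both, as worded | 5.2 in the implied direction | Both, in the implied direction |
|---|---|---|---|---|---|
| 6 target causes | met | excluded | 0 of 6 pass | not excluded | 6 of 6 pass |
| 9 listed causes | not met | not excluded | 0 of 9 pass, stopped by 5.1 alone | excluded | 0 of 9 pass, stopped by both |

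As worded, the bullet removes all six target causes and catches none of the nine it lists. Reversed, it agrees with Sections 1.2, 5 and 5.1 in every row.

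Patients with two causes, taking ILD with OSA as the example, and assuming that an established diagnosis of PH from ILD can be on record while OSA contributes:

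| Primary cause | 5.1 diagnosis | 5.2 as worded | 5.2 in the implied direction |
|---|---|---|---|
| ILD | met | excluded | not excluded |
| OSA | can be met, since 5.1 does not ask which cause is primary | not excluded | excluded |

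Here 5.1 does not settle the matter and the stem gives the wrong answer both times.

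Other criteria that might catch a coexisting listed cause:
- Left heart disease is partly covered by the PCWP and ejection fraction limits and the valvular exclusion.
- Airflow obstruction is partly covered by the FEV1/FVC and FEV1 limits.
- Nothing else in 5.1 or 5.2 addresses OSA, HIV or veno-occlusive disease.
- The requirement that a cause be primary appears nowhere else in the two sections.

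**The case against.** The strongest reply is that nobody would apply the sentence literally. The target population is stated consistently in three places, every listed cause lies outside it, and the trial has one site. With some strain the stem can even be read as PH other than the study's own PH, namely PH due to the listed causes. And the note leaves overlapping syndromes to the recruiting physician whichever way the stem runs. Most of this stands: the intended direction can be recovered, and this is not evidence that a different population was planned. But the strained reading is not what the sentence says, and the note gives a physician discretion without a correct written rule to exercise it against.

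Several stronger readings are tempting and are not supported:
- *The unwanted causes are let in.* A patient with only a listed cause fails 5.1.
- *The protocol admits nobody.* The literal reading shows that the text is wrong; it does not forecast enrolment.
- *Staff must guess the direction.* Sections 1.2, 5 and 5.1 supply it.
- *Largely post-capillary or COPD-driven disease would enter the primary endpoint.* Section 5.1 requires precapillary PH with PVR of at least 400 dynes * sec * cm⁻⁵ and PCWP of at most 20 mmHg, and 5.2 adds the ejection fraction, valvular and spirometry limits.
- *The left ventricular risk factor bullet has the same fault.* "Participants must not have 3 or more of the following left ventricular disease / dysfunction risk factors" is phrased as a prohibition inside an exclusion list, which is awkward, but it has one sensible meaning: three or more makes a patient ineligible.
- *The per-protocol analysis is compromised.* Section 10.1 defines that population, but Sections 10.3 to 10.5 analyse every endpoint in the ITT population.
- *The effect can be sized by one participant's share of a small arm.* That share is the same for any participant; it says nothing about how many ineligible patients the wording would admit, or about bias.

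**Conclusion.** The point holds as a drafting error in an operative eligibility criterion. The stem says the opposite of what Sections 1.2, 5 and 5.1 require: as worded it excludes all six target causes and none of the nine listed ones, and in the implied direction these counts become none and all nine. Its practical reach is limited to mixed-aetiology patients, for whom it is the only written standard on the primary cause.

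No sample size, estimate or analysis in the plan depends on this text, and the documents give no basis for a number of affected participants. The conclusion rests on the natural grammatical reading of the stem and on the assumption that a target diagnosis can be established alongside a listed cause. The eligibility checklist is not among the documents, so whether staff work from the reversed wording is unknown.

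**What to change.** Reconcile the stem with Sections 1.2, 5 and 5.1 by deleting the words from 'for reasons' to 'the pulmonary hypertension', so that it reads: *Participants with a diagnosis of PAH or PH primarily due to any of the following:*. Leave the list and the overlap note unchanged. Carry the same wording into the eligibility checklist, and confirm which direction any checklist already in use follows.

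The cost is one sentence stem in the next amendment and a matching checklist edit. No threshold, list item or analysis changes. Recasting the left ventricular bullet to match its neighbours is an optional matter of style.
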